4.2 Objectives and Hypotheses

Phase 1: Design and Development of the Virtual Reality Experience

1. Work with an interdisciplinary team to collaboratively develop an engaging prototype (V1.0) that models the MRI environment and experience at BCCH.

Phase 2: Technology Evaluation and Comparative Assessment

2. Evaluate the effectiveness in pre-procedural preparation through a comparative assessment against other modes of delivery currently offered at BCCH – including pre-procedural instructional booklet, and mock MRI with CLS.
 - a. *Hypothesis:* There will be differences in outcomes between the virtual reality group and the booklet group.
 - b. *Hypothesis:* There will be no difference in outcomes between the mock MRI and virtual reality simulation groups.
 - c. *Hypothesis:* Children will prefer the virtual reality and simulation exercises to booklet preparation.

Phase 3: Economic Evaluation and Impact Modeling

3. Evaluate costs and benefits of the VR solution and status quo; and conduct economic modelling on the prospective impact of operational integration.

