A minimum of 93 participants (31 participants per group) aged 4-to-13 will be recruited through convenience sampling, consented, and randomized by staff to one-of-three preparation programs (VR, mock MRI, or booklet). Details of the comparison groups are outlined in **Table 4**. Given the restricted availability of the simulator, child life specialists, and the availability of participants, we are unable to fully randomly allocate participants. As such, participants will be randomly assigned to the intervention options available according to their individual availability (using Research Randomizer <https://www.randomizer.org/>). For example, if a participant is available on a Thursday that virtual reality and booklet are available, they will be randomly allocated to one of these interventions.

This phase will have open recruitment to all children and adolescents interested in participating, such that participants may not be BCCH patients scheduled for an MRI. This recruitment strategy was selected due to the resource constraints associated with limiting the evaluation group to MRI patients only.

Table 4. Details of the comparison groups.

	VR Simulation	MRI Preparation Booklet	Mock MRI
Facilitator	Research Assistant	Research Assistant	Child Life Specialist
Location	BCCH	BCCH	Simulation Room
Content	Refer to The Virtual Reality Simulation	Refer to MRI Preparation Book	Individualized intervention in physical simulator.

The different interventions will be held in separate private rooms located in BCCH, such that the VR and booklet groups will not have prior exposure to the imaging centre or the simulation room in advance of their assessment. This is to simulate our intended delivery in hospital, medical office, or clinic settings but minimize alternative explanations associated with testing in the simulation room where assessments will take place (previously described in **Table 3**).

Data will be collected throughout the implementation process (**Figure 3**). The predictive variables (demographics and relevant history, and delivery type) will be captured at the start of the session. The primary outcome variable is likelihood of success (pass/fail) of the MRI simulation, and will be measured at the end of the assessment. Anxiety will also be measured at three time points. Usability testing will be conducted throughout to capture possible quality improvements and amendments to each of the program delivery modes.

Inclusion/Exclusion Criteria

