- 9) Participants will be informed that they will now be completing a simulation test with the MRI scanner. Participants will be reminded of their free and informed ongoing consent.
- 10) The participant will be transferred to the simulation room, located in the medical imaging center at BCCH. Upon entering the simulation room, participants will verbally complete the VPT with staff (during test). In parallel, parents will complete the Short STAI on the iPad. (5 minutes)
- 11) Participants will be guided through a mock MRI and be assessed using MoTrack®, an objective head motion tracking system.³² The simulation will be completed over 20 minutes and will involve progression through the “MRI procedure”, remaining in the bore for 8 minutes. All participants will receive the same type of simulated scan. We will not be simulating any invasive procedures that can sometimes occur during the MRI (i.e. an IV or intravenous contrast liquid). Please note that this assessment involves a mock procedure using the simulator, not a real MRI.
- 12) Immediately following the simulation, participants will verbally complete the VPT with staff (post-test). In parallel, parents will complete the Short STAI on the iPad. (10 minutes).

- 13) Users will be asked to indicate on the *Smileyometer* how they thought the preparation activity was overall in preparing them for the MRI. Parents/guardians will be asked to complete the USE Questionnaire.
- 14) Staff will ask the user open-ended questions on the preparation materials according to three separate criteria of fun, ease of use, and how good it was for learning about the MRI experience. The final usability assessment will take a total of 10 minutes.
- 15) After the session is "complete", children will be told that they "happen to have some time left" so they can play with any of the preparation materials offered (VR, Mock MRI, Booklet) for 5-minutes if they want to "because they did so well during the activity." This will give children a natural choice selection and will be used to gauge preferences for the activities.
- 16) A verbal session debrief will include an opportunity for questions to mitigate any residual feelings of discomfort or anxiety that may arise from the project's activities.

Outcome Measures

The measures used to evaluate the intended outputs and outcomes associated with this project are outlined below (**Table 4**).

Table 4. Outputs and outcomes associated with the project.

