A priori power analysis was calculated using G-Power.³⁸ A total sample size (N) of 93 was calculated to be needed across the 3 groups (31 per group), with a significance level of 95% ($\alpha=0.05$) and a power of 90% ($\beta=0.10$), allowing for a 10% drop out rate. An effect size of 0.2 was selected to reflect the research suggesting that CLS preparation can reduce sedation rates by 20%.

Descriptive analysis will be conducted on the demographics and relevant history data.

Differences in predictive success of the MRI simulation ranking scores (pass or fail) will be examined using a Repeated Measures ANOVA, within-between interaction for three timepoint measurements (before, during, after) of anxiety and delivery type (VR, mock MRI, booklet). In the case of an off-normal distribution, non-parametric tests may be used. Multivariate analysis will test for possible confounding effects (demographics and relevant history).

Survey data (USE questionnaire, Smileyometer) will be analyzed using means and standard deviations of all respondents for each category of the questionnaires. The proportions of the participants reporting high, medium, or low levels will also be calculated.

Study staff will document responses to the guided survey and read the recorded answers back to participants to verify accuracy and elicit possible further reflection. All of the qualitative data will be uploaded to NVivo by study staff. When complete, study staff will code the information to identify major themes, gaps, barriers within the existing approach and the team will devise recommendations for improving the preparation programs. The phases of this process include:

- Familiarizing yourself with the data

- Generating initial codes
- Searching for themes
- Reviewing themes
- Defining and naming the themes
- Triangulation with other findings and producing a report

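### The primary outcome, a pass/fail result recorded once per child, is assigned a repeated-measures ANOVA of anxiety, so it has no usable test, effect measure, interval or VR contrast

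*Combined protocol and SAP*

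**What the plan says.** Section 4.4, in the protocol for evaluating the simulator, defines the primary outcome: "The primary outcome variable is likelihood of success (pass/fail) of the MRI simulation, and will be measured at the end of the assessment". Under Primary Measures, a child fails on reaching 3 mm of movement in x, y or z. Step 11 of the Implementation Plan describes one assessed scan per child, after preparation: "Participants will be guided through a mock MRI and be assessed using MoTrack". No baseline scan is described.

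The Analysis and Interpretation part assigns the method: "Differences in predictive success of the MRI simulation ranking scores (pass or fail) will be examined using a Repeated Measures ANOVA". The same sentence specifies the model as a "within-between interaction for three timepoint measurements (before, during, after) of anxiety and delivery type (VR, mock MRI, booklet").

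Three other statements bear on the analysis:

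- "In the case of an off-normal distribution, non-parametric tests may be used".
- "Multivariate analysis will test for possible confounding effects (demographics and relevant history").
- Earlier in section 4.4: "The predictive variables (demographics and relevant history, and delivery type) will be captured at the start of the session".

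Section 4.2 sets two comparisons for VR. The first is against the booklet: "There will be differences in outcomes between the virtual reality group and the booklet group". The second is against mock MRI, where no difference is expected. Neither says which outcomes are meant.

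The list of primary outcomes varies. The definition above gives pass/fail alone. The outcomes table (the second table numbered 4) adds the Venham test and the Short STAI under Primary. The text after that table keeps the Venham test under Primary Measures but puts the Short STAI under Secondary Measures.

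**The concern.** A within-between interaction needs a response measured at each level of the within-subject factor. Anxiety is measured three times and pass/fail once, so the specified model is a model of anxiety. Followed as written, it would answer an anxiety question under the label of predictive success.

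Three things are at stake. The test, effect measure and interval for the primary outcome would have to be chosen later, possibly after the data are seen. A significant anxiety interaction could be reported as a difference in success at the scan. A non-significant comparison of VR with mock MRI could be read as confirming that they do not differ, although no margin is set. In addition, the power statement ties its effect size to a 20% reduction in sedation rates, so a reader could take the 90% power to apply to pass/fail.

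**Working it through.** **1. The plan's own sample size.** Inputs from Analysis and Interpretation: 3 groups, α = 0.05, power 90%, effect size 0.2, 10% drop-out, N = 93. The within-between interaction with m = 3 time points and k = 3 groups uses a noncentral F with λ = f²·N·m·ε/(1−ρ), df1 = (k−1)(m−1)ε and df2 = (N−k)(m−1)ε. The plan does not give the correlation ρ or the sphericity correction ε.

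| Reading, effect size 0.2 | N before drop-out | N after 10% |
|---|---|---|
| Interaction, ρ 0.5, ε 1 | 69 | 77 |
| Interaction, ρ 0.5, ε 0.75 | 84 | 93 or 94 |
| Interaction, ρ 0.37–0.38, ε 1 | 84 | 93 or 94 |
| Three-group chi-square, w = 0.2 | 318 | – |

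So 93 is compatible with an anxiety interaction under unstated settings and should not be called wrong. It does not fit a comparison of pass/fail.

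**2. Degrees of freedom.** The omnibus interaction has (3−1)(3−1) = 4 df. One pair of groups over three time points has (2−1)(3−1) = 2 df. One pair compared on pass/fail has 1 df. The 4-df test isolates neither VR comparison.

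**3. Assumptions for pass/fail.** Evaluable children per arm: 31 × 0.9 = 27.9, taken as 28. Anchor pass rate: the simulator results in Table 2 of section 3.0, (283 + 8)/344 = 84.6%. The 20-point difference is assumed. Tests are two-sided at 0.05.

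**4. Power and precision for a 20-point difference.**

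Power = Φ((d − 1.96·√(2p̄(1−p̄)/n)) / √((p1q1 + p2q2)/n)), where p̄ is the mean of the two rates.

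At 84.6% against 64.6%, p̄ = 0.746:

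- Null term: 1.96 × √(2 × 0.746 × 0.254/28) = 0.228.
- Standard error: √((0.1303 + 0.2287)/28) = 0.1132.
- Power = Φ((0.200 − 0.228)/0.1132) = 0.40.
- 95% half-width: 1.96 × 0.1132 = 0.222.

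| Pass rates (%) | Power, n = 28 | Fisher exact | Half-width (points) | n per arm for 90% |
|---|---|---|---|---|
| 60 vs 40 | 32% | 22% | 26 | 130 |
| 84.6 vs 64.6 | 40% | 30% | 22 | 98 |
| 90 vs 70 | 46% | 33% | 20 | 82 |
| 95 vs 75 | 56% | 39% | 18 | 65 |

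**5. VR against mock MRI with equal true rates.** Half-width = 1.96·√(2pq/n) = 1.96 × √(2 × 0.846 × 0.154/28) = 0.189, about 19 points.

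**6. Effect of allocation by availability.** Children are randomized only among the options open to them. If only children with both options open count in a contrast, n falls by an unknown amount. With 21 or 14 per arm (assumed), power at the anchor is 31% or 22%, and the half-width is 26 or 31 points. With equal rates the half-width is 22 or 27 points.

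**The case against.** The two VR comparisons are named in section 4.2, and the economic section (4.5) plans to report predictive non-sedation rates and to divide cost differences by differences in effect. A between-group difference in pass rate is therefore implied. That is fair as far as it goes. But section 4.5 gives no test or interval for that difference, and its uncertainty analysis covers programme variables only. The analysis section does not carry the section 4.2 comparisons through to pass/fail.

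The non-parametric clause might be read as a fallback. It is optional, depends on non-normality and names no test. The multivariate analysis is directed at confounding.

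Several objections to the figures stand in part:

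- The 84.6% comes from clinical referrals, whereas this trial recruits openly, and the documents do not say that those passes used the 3 mm rule. This is why a range is shown.
- The 20% in the introduction concerns preparation programmes and sedation, not VR against booklet.
- The plan calls 93 a minimum, and loss within a single two-hour session may be below 10%. With 31 per arm, power at the anchor is 44% (Fisher exact 34%) and the half-width 21 points, so the conclusion does not change.
- At the anchor an arm of 28 has about 28 × 0.154 = 4 failures, so stratified analysis would be sparse.

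The study is also exploratory in tone. That would excuse wide intervals, but not a primary analysis that does not analyse the primary outcome.

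**Conclusion.** The concern holds and must be fixed. The core is textual and rests on no assumed number: a binary result recorded once cannot be the response in an interaction over three anxiety time points, and nothing else specified supplies a test, effect measure or interval for it. The missing VR contrasts, the missing margin and the conflicting lists of primary outcomes (one, two or three measures) are also matters of text.

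The size of the power gap is illustrative. It depends on the assumed 20-point difference, the assumed pass rates and 28 evaluable children per arm. Over the ranges shown, power for pass/fail is well short of 90%, and about 65 to 130 evaluable children per arm would be needed to reach it.

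**What to change.** 1. Replace the pass/fail sentence in Analysis and Interpretation with wording such as:

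> Pass/fail will be compared between VR and booklet, and between VR and mock MRI, as risk differences with 95% confidence intervals, accounting for the set of options open to the child at allocation (for example, by stratification). VR versus mock MRI will be reported as an estimate with its interval, and no claim of no difference will be made unless a justified margin is prespecified.

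   Name the interval method as well, choosing one that copes with few failures, and say which contrast takes precedence.

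2. Keep the repeated-measures model, or a baseline-adjusted model, for the Venham score. Report the same two contrasts at a named time point, for example the during-test score adjusted for the pre-test score.

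3. Make the primary outcome agree across the outcome definition, the outcomes table and the measures headings. Add a multiplicity rule if more than one outcome is primary.

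4. State that the 90% power does not apply to pass/fail. Give the expected half-width at N = 93, about 18 to 26 points under the assumptions above, and note that it is wider if children without both options open do not count in a contrast.

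The cost is wording, slightly more analysis work and one extra recorded field for the options open at allocation. Section 4.4 says recruitment was broadened after low enrolment, so that field may have to be reconstructed for children already allocated, and this may not always be possible. No added enrolment is required. The drawback is a less favourable statement of power.

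### The three-reading repeated measures ANOVA of anxiety would drop any child missing one reading; a mixed model on all available readings is safer and costs almost nothing

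*Combined protocol and SAP*

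**What the plan says.** All references are to section 4.4 unless stated.

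- **Method.** Analysis and Interpretation specifies a "Repeated Measures ANOVA, within-between interaction for three timepoint measurements (before, during, after) of anxiety and delivery type". The sentence opens with the pass/fail result, which is a separate matter. The part at issue here is the three anxiety readings by delivery type.
- **Fallback.** "In the case of an off-normal distribution, non-parametric tests may be used". The trigger is the shape of the distribution, not missing readings, and no test is named.
- **Drop-out.** The sample size of 93 (31 per group) is described as "allowing for a 10% drop out rate". Drop-out appears nowhere else. No analysis population, missing-data rule, imputation or sensitivity analysis is given. No complete-case rule is written down either.
- **Timing of the VPT (Implementation Plan).** The first reading is at step 3, before allocation is revealed. The second is at step 10, on entering the simulation room. For the third, step 12 says: "Immediately following the simulation, participants will verbally complete the VPT with staff (post-test".
- **Withdrawal.** At step 9, after preparation and before the second reading, "Participants will be reminded of their free and informed ongoing consent".
- **Status.** The outcomes table lists the VPT, together with the Short STAI, as primary. The text below it puts the parents' Short STAI under secondary measures.

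**The concern.** Deletion of incomplete records is a property of the named method rather than a stated rule, but nothing in the plan offsets it. The mock scan lies between the second and third VPT readings. A child who gives the step 10 score, stops, and gives no post-test is removed whole. The step 10 score follows preparation and precedes the scan, so it carries direct information on how well each mode prepared the child.

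The 10% allowance replaces lost numbers but does not correct selection. The Introduction links anxiety to failure to complete imaging, so loss that depends on anxiety is foreseeable. If it occurs, the less well prepared arm would lose more of its anxious children, and the arms would look more alike than they are. Section 4.2 predicts a difference between VR and booklet and no difference between VR and mock MRI. Attenuation works against the first prediction and in favour of the second. Section 4.5 also carries anxiety reductions into the cost-effectiveness ratios.

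**Working it through.** **1. The plan's own figure.** Inputs from Analysis and Interpretation: 3 groups, 3 readings, effect size 0.2 (read as Cohen's f), alpha 0.05, power 0.90. For the within-between interaction as in G*Power:

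- lambda = f² × N × m × eps / (1 − rho)
- df1 = (k − 1)(m − 1) × eps
- df2 = (N − k)(m − 1) × eps

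The correlation rho and the sphericity factor eps are not stated.

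- With rho 0.5 and eps 1, N = 69. With drop-out this is 69 × 1.1 = 75.9 (76) or 69 / 0.9 = 76.7 (77), not 93.
- With rho 0.37-0.38 and eps 1, or rho 0.5 and eps 0.75, N = 84. Then 84 × 1.1 = 92.4 (93) or 84 / 0.9 = 93.3 (94).

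So 93 is attainable but is not determined by the stated inputs.

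**2. Cost in numbers.** 93 × 0.9 = 83.7, so about 84 complete records, or 31 × 0.10 = 3.1 children lost per arm. With rho 0.5 and eps 1, lambda falls from 0.04 × 93 × 3 / 0.5 = 22.3 to 0.04 × 84 × 3 / 0.5 = 20.2.

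| rho (assumed) | Power, N = 93 | Power, N = 84 |
|---|---|---|
| 0.5 | 0.976 | 0.960 |
| 0.3 | 0.903 | 0.866 |
| 0 | 0.757 | 0.705 |

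The 10% allowance is meant to absorb this loss. Selection is the remaining issue.

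**3. Possible bias.** The documents give no SD, correlation, means or drop-out pattern, so every input here is an assumption: VPT 0-8, SD 2, correlation 0.5, baseline mean 3 in both arms, step 10 means 2.5 (VR) and 3.5 (booklet), scores rounded and clipped. The post-test is lost with a logistic probability that rises by 0.5 to 1.5 per VPT point at step 10, set to a given overall loss. The quantity is the VR-booklet difference in change from baseline to step 10, which is 0.93 points with full data.

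| Loss after step 10 | Related to anxiety? | Attenuation among complete cases |
|---|---|---|
| 10% | yes | 4-11% |
| 5% (half of the 10% are no-shows) | yes | 2-7% |
| 10% | no (random) | 0 |

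At 10% the difference falls to between 0.93 × 0.96 = 0.89 and 0.93 × 0.89 = 0.83, a bias of 0.04 to 0.10 points. The standard error of this difference at 31 per arm is about 0.49. (Before clipping, the SD of change is √(2 × 4 × 0.5) = 2, and 2 × √(2/31) = 0.51.) The bias is therefore 0.04/0.49 = 0.08 to 0.10/0.49 = 0.20 of a standard error.

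**4. Second illustration.** This used normal readings, correlation 0.5 and a true difference of 0.50 SD at the second and third readings. With about 12-14% anxiety-related loss, complete cases gave 0.43-0.46 at the second reading and 0.47-0.48 at the third. Keeping partial records gave about 0.50 at both. With 10% random loss both approaches gave 0.50.

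**The case against.** A reader might infer that the most anxious children will leave and that this hides a real VR-booklet difference. The documents do not support that, for these reasons:

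- The step 9 reminder comes before the step 10 reading. A child who leaves there has only a baseline score, so no step 10 score is deleted, and a mixed model recovers almost nothing about that child's change.
- No section says that a child who stops the scan skips the post-test. Exceeding the 3 mm movement threshold does not remove it.
- Allocation follows consent by telephone or email, before attendance. Part of the 10% may be no-shows with no readings, whom no model recovers. About 3 per arm is therefore an upper figure.
- The Introduction's statement concerns imaging in general. This study is one two-hour session with a mock scan and no invasive procedure, in volunteers who need not be patients awaiting MRI.
- The bias is small beside sampling error. Under the assumptions of step 3 of the working, power for that one contrast is about 0.42 with 10% random loss and 0.36-0.40 with anxiety-related loss. The contrast simulated is also not the planned three-reading interaction test.
- For parents the mechanism is uncertain. The Short STAI paragraph puts all three readings at baseline, after the intervention and before the mock MRI, whereas the Implementation Plan puts them at steps 3, 10 and 12.

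All of this stands, and it limits the size and certainty of the bias. It does not remove the gap: the named method discards partial records, and the plan offers nothing in its place. The non-parametric fallback does not help, since a common choice such as Friedman's test also needs complete rows.

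**Conclusion.** The concern holds as a modest weakness in the choice of analysis. The planned method would discard readings already collected from any child who misses one, in a study that expects 10% drop-out and lists the VPT as a primary measure. Attenuation is about 4-11% if the whole 10% is anxiety-related loss after step 10, about 2-7% if half of it is, and nil if loss is random. At most this is about 0.2 of a standard error at 31 per arm. These sizes rest on assumed SD, correlation, means and drop-out slope. That loss will be related to anxiety is plausible but not established. The change is worth making because it is better whenever partial records exist and costs very little if few do.

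**What to change.** - Replace the repeated measures ANOVA for the VPT with a linear mixed model for repeated measures: arm, time and arm-by-time, with unstructured covariance, including every allocated child with at least one reading.
- Reconcile the timing of the Short STAI between its own paragraph and steps 3, 10 and 12, then use the same model for it.
- Report withdrawals by arm, step and reason, with no-shows separate from children who stop during the session.
- Add a sensitivity analysis for loss that depends on the unseen post-test, which the mixed model does not correct.
- If a reading is offered when a child stops, with consent respected, flag it and use it only in that sensitivity analysis. It measures a different situation from a post-test after a completed simulation.

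The cost is a revised analysis paragraph, standard software and slightly more analysis work, with no added visits. The model relies on data being missing at random, which is a weaker assumption than the one behind a complete-case analysis.
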